#### 3. Abstract:

Although compelling evidence exists that high doses of mother's own breast milk (mother's own milk; MOM) improves infant health, breast pump dependent (need to use a breast pump to obtain milk for infants too ill or preterm to breastfeed) mothers of critically ill infants often provide insufficient amounts of MOM to support these benefits. Insufficient MOM has its origins during the first 14 days postpartum, a critical window that includes secretory activation (SA; milk coming in; lactogenesis II) and the achievement of coming to volume (CTV; providing ≥ 500 mLs/day of MOM by day 14 postpartum). For all lactating mothers, SA must be achieved for lactation to continue, and achievement of CTV predicts provision of MOM through to neonatal intensive care unit (NICU) discharge in preterm very low birthweight (VLBW; <1500 g birthweight) infants. For this study, we posit that alternate breast pump suction patterns (BPSP; suction rate, intensity, and rhythm) may facilitate achievement of CTV in mothers who have achieved SA, but whose daily pumped MOM volumes indicate a high risk of not achieving CTV. Therefore, the overall objective of this study is to compare the clinical effectiveness of three different breast pump suction patterns on lactation outcomes, including achievement of SA, among pump dependent mothers of critically ill infants who demonstrate faltering lactation after achievement of SA. At 6-8 days postpartum, 90 pump dependent mothers of critically ill infants who have achieved SA, but demonstrate faltering lactation (<350 mLs/day pumped MOM volume), will be randomized to use one of three different BPSPs with two groups having alternative BPSPs and one group using the current practice standard for 7 days. Study outcomes will include the following; (1) pumped milk volume, (2) secondary lactation outcomes (whether or not mothers achieve CTV by day 14-15 postpartum, maintenance of secretory activation, MOM removal efficiency, and lactation duration); (3) maternal perceptions of comfort, effectiveness, efficiency, and convenience of the BPSPs, and (4) proportion of feedings consisting of MOM consumed by infants. Two exploratory aims will explore potential benefits of the 3 BPSPs on lactation outcomes of mothers with co-morbidities known to negatively affect the above-mentioned lactation outcomes and whether mothers at risk of suboptimal lactation who use an alternate BPSP achieve the same lactation outcomes as do mothers who do not demonstrate faltering lactation.

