The NICU at UF Shands admits infants that are racially diverse regardless of private or Medicaid insurance coverage. All mom that meets the above criteria would be eligible for enrollment. Informed consent will be obtained by mothers in their postpartum hospital room or in the NICU while visiting their infant prior to 48 hours postpartum. The informed consent includes mother's permission to access their infant's chart to collect information up until infant's discharge. The infant has no study interventions. In the rare instance that an infant breastfeeds, intake will be determined through test weighting (infant weight pre and post breastfeeding). Prior to the mother's hospital discharge, she will be provided an empty payment card where participants will receive compensation, by adding payments for completing study events, listed below. After enrollment, a 2-minute maternal interview will be used to collect information to determine pre-pregnancy BMI and other factors that might impact lactation success (Appendix B). Information will be collected related to pumping frequency and pumped milk volume prior to enrollment (Appendix I). All enrolled mothers will be provided breast pumping instructions to optimize their pumping behaviors prior to achievement of secretory activation. This 30-minute optimization session will be provided by a Research Nurse Coordinators, who is also an International Board-Certified Lactation Consultant (IBCLC). The instructions will be standardized using a score card, which provides prompts for education discussion and video links about pumping practices, breast and nipple assessment, breast shield sizing and comfort. (Appendix F). A daily sample of 0.3 mL of pumped MOM (if mother has pumped at least 5mL/day) will be tested for MOM sodium level as an indicator of secretory activation. At day 6-8 postpartum, mothers at high risk of suboptimal lactation will be identified and randomized to one of three BPSPs Mothers will be determined to be at risk if they have (1) achieved secretory activation (change from small volumes of colostrum to large volumes of more mature milk; determined by a milk sodium level < 20 mM) and (2) have a pumped milk volume < 350 mL/d. Mothers who are identified as being not at risk for suboptimal lactation (have achieved secretory activation and their pumped milk volume is > 350mL/d) will not be randomized but will continue with standard care regarding BPSPs, and continue to have data regarding lactation collected. Mothers who do not reach SA, determined by a milk sodium level > 20 mM, will be withdrawn from the study and referred to the UF Shands Lactation Team. All mothers that achieve SA, will be provided a second 30-minute standardized breast pumping optimization session with instructions by a Research Nurse Coordinator who is an IBCLCs at day 6-8 postpartum. Mothers will complete the Maternal Perceptions Survey (Appendix K/Part A only) before starting new pattern. If randomized, Moms will complete the Maternal Perception Survey (Part A/B) on Day 9-11. A score card, designed for mothers who have already achieved secretory activation, includes educational prompts and video links regarding milk volume, pumping behaviors, breast and nipple assessment, flange fit and comfort will be utilized. (Appendix G). Should a mother be unable to obtain transportation to the NICU, they will be provided transportation through Uber Health, provided they live within a 60-mile radius of UF Shands due to cost limitation of study.

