
Mothers will be provided a payment card for amount listed following completion of the listed study event(s).

- 1. All mothers enrolled: optimization pumping session with the study Research Nurse Coordinator IBCLC, completion of the first MAACL, maternal interview, and lactation experience questionnaire. (\$25.00)
- 2. All mothers that achieve SA: Following completion of the second pumping optimization session with the study Research Nurse Coordinator IBCLC and completion of Maternal Perceptions Survey (Part A only) (\$25.00)
- 3. All mothers that do not reach SA, will be withdrawn from the study and not eligible for further compensation.

4. Following completion of the second MAACL, lactation experiences survey, maternal perception survey (if randomized) and return of all "loaned" breast pumps (\$50.00)

Total Compensation: Moms withdrawn at Week 1 (did not reach SA) \$25.00. All other moms (reaching SA) will receive up to (\$100)

**Sample Size Determination:** With 30 dyads (mom and infants) will randomized, using the block method, to each intervention group (2 alternate, one standard care), assuming a = 0.02 (Type I error rate), two-sided; independent sample t-test comparison of means (adjusted for multiple comparison between 3 groups); equality of variance between groups with 30 mothers per group we will have 80% power to detect a difference of 300 ml (effect size of 0.84; sd=350.0) between the groups.

**Randomization:** Those mothers who have been identified as being at high risk for suboptimal lactation will be randomly assigned using Block randomization to use one of three different BPSPs [BPSP1, BPSP2, or Symphony Plus BPSP (Standard Care)] for 7 days.

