## Research Procedures and Analyses by Specific Aim.

**Aim 1**: *The primary aim of this study* is to compare the clinical effectiveness of 3 different BPSPs on pumped milk volume during Days 8-15 postpartum.

Mothers will have access to a hospital grade breast pump (Medela Symphony Plus) while hospitalized and when visiting their infant in the NICU (standard policy). Upon hospital discharge, all mothers will be provided the same hospital grade breast pump for home use. At 6-8 days postpartum, those mothers who undergo randomization, will be provided a hospital grade SMART pump (Medela, AG, Switzerland) as a substitute for the standard hospital breast pump. The SMART pump (the same breast pump used as standard care) has been adapted to electronically measure, record and store both pumping behaviors and weighed MOM volume (measured ± 0.1g; 1 g=1 mL). A card will be inserted into the SMART pump which will program the pump to either use BPSP1, BPSP 2, or Standard Plus). Mothers will be blinded to the BPSP used. Information is stored and the embedded computer chip is downloadable into a customized computer program (on a secure College of Nursing computer) at the termination of data collection. A SMART pump with the same randomized pattern will also be placed at their infant's bedside in the NICU to facilitate pumping in the NICU. Mothers will be provided a key tag to use prior to using the SMART pump to ensure only her pumping information is stored on the embedded computer chip. All mothers will be assisted to obtain a permanent breast pump for home use after study completion as per usual hospital care. Mothers that have been withdrawn from the study, at week 1, for not reaching SA, will be allowed to use the Medela Symphony Plus for 2-weeks, as needed.

Pumped milk volume will be measured daily using the following two method;

- (1) Mothers will weigh each bottle of MOM using the SMART pump and this information will be recorded and stored (only those mothers who are randomized and only from day 8-15).

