vials of MOM brought to the NICU and place the sample onto the sensor of an ion selective electrode analyzer (HORIBA, Japan) which is a hand-held machine used for sodium and potassium analysis (see photo), has been validated for accurate analysis of human milk sodium and potassium levels, and will be calibrated prior to every analysis. Although both sodium and potassium are secreted into milk via transcellular pathways, sodium but not potassium is also transferred from the maternal circulation via patent paracellular pathways. Thus, it has been suggested that a milk sodium to potassium ratio would standardize sodium level for individual women. While no differences have been reported between the ability of sodium alone versus a Na:K ratio to predict pumped milk volume, we will also measure potassium levels. (Appendix H) To ensure accuracy, individuals performing sodium analysis will be trained and evaluated prior to beginning analysis and quarterly. Our team is highly skilled in milk collection, processing and analysis.

Rate of increase in daily pumped MOM volume, achievement of secretory activation (Yes/No), and cumulative MOM volume over days 1-7 and 8-15 postpartum. MOM volume will be measured as discussed in Aim 1 and each of the outcomes determined.

Milk removal efficiency. Efficiency of milk removal will be determined by mls of MOM pumped per minute of pumping (cumulative per day and cumulative over days 8-15). Minutes of pumping is measured and recorded on the SMART pump (Appendix M).

Lactation Duration. Number of days a mother lactates (either via breastfeeding or expressing MOM) during her infant's hospitalization and whether or not she is lactating at infant discharge will be collected. Mothers will be determined to have ceased lactation when they are no longer bringing MOM to the NICU, are not placing the infant to breast for nutritive or non-nutritive sucking, and states they are no longer lactating when questioned. If still lactating at their infant's NICU discharge, mothers in all groups will be questioned regarding their continued lactation through monthly text message hyperlinked surveys via the Qualtrics platform until their infant is 6 months of age or she has ceased lactation. If a mother ceased lactation within the past month, she will be asked the week within the past month she discontinued lactating (Appendix J).

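### The stated 7 days of allocated pattern use cannot cover the day 8-15 primary window for mothers who start on day 6 or 7; use through day 15 appears to be intended and should be written

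*Protocol*

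**What the plan says.** **Duration.** Two places state how long the allocated pattern is used. The Randomization paragraph under Sample and Setting assigns mothers "to use one of three different BPSPs [BPSP1, BPSP2, or Symphony Plus BPSP (Standard Care)] for 7 days". The Abstract describes two groups on alternative patterns and "one group using the current practice standard for 7 days".

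**Start.** Sample and Setting says: "At day 6-8 postpartum, mothers at high risk of suboptimal lactation will be identified and randomized to one of three BPSPs". Research Procedures, Aim 1, says: "At 6-8 days postpartum, those mothers who undergo randomization, will be provided a hospital grade SMART pump". Table 2 places randomisation over days 6 to 8.

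**Outcome windows.** The primary aim "is to compare the clinical effectiveness of 3 different BPSPs on pumped milk volume during Days 8-15 postpartum". Volumes weighed on the SMART pump are taken from "only those mothers who are randomized and only from day 8-15". For efficiency, "Minutes of pumping is measured and recorded on the SMART pump", and Table 1 schedules that measure daily on days 8-15.

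**End of pump use.** No sentence dates it. Research Procedures, Aim 1, says: "All mothers will be assisted to obtain a permanent breast pump for home use after study completion as per usual hospital care". Table 2 is titled as a 15-day timeline.

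**CTV cut-off.** The definition in the Abstract and the Aim 2 procedures both require at least 500 mL by day 14. The Abstract's outcome list, the Background and Aim 2 under Specific Aims all use day 14-15.

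**The concern.** Duration of use is part of the definition of the intervention. The only two sentences that state it give a figure that does not fit the start days and the primary window given elsewhere.

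If staff follow those sentences, mothers who start on day 6 or 7 come off the allocated pattern before the window closes. Their remaining daily volumes would still count towards the primary outcome. Those days fall at the end of the window, on or next to day 14, when CTV is judged. SMART pump minutes, which efficiency needs through day 15, would also be at risk.

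If staff follow the schedule and leave the pump in place to day 15, mothers use the pattern for longer than the protocol says, and the protocol misdescribes what was tested.

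**Working it through.** **Inputs.** Start day s = 6, 7 or 8 (Sample and Setting; Research Procedures, Aim 1; Table 2). Stated duration 7 days (Abstract; Randomization). Window days 8-15, so 15 − 8 + 1 = 8 daily totals (Specific Aims, Aim 1; Research Procedures, Aim 1).

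**Formulas.** The protocol does not say how the 7 days are counted, so both ways are shown.
- Calendar days: last day on pattern = s + 6.
- Elapsed days: last day on pattern = s + 7.
- Window days off pattern = 15 − last day.
- Use through day 15: calendar days on pattern = 15 − s + 1 = 16 − s.

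| Start day | Last day, calendar count | Window days off pattern | Last day, elapsed count | Window days off pattern | Days on pattern if used through day 15 |
|---|---|---|---|---|---|
| 6 | 12 | 3 of 8 | 13 | 2 of 8 | 10 |
| 7 | 13 | 2 of 8 | 14 | 1 of 8 | 9 |
| 8 | 14 | 1 of 8 | 15 | 0 of 8 | 8 |

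For a day 6 or day 7 start, the three statements (start, 7 days, window to day 15) cannot all hold on either count. For a day 8 start they hold on the elapsed count and miss by one day on the calendar count.

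**Which statement is wrong?** On one side stand the two sentences giving 7 days. On the other:
- SMART recording and the efficiency measure run to day 15, and both need the SMART pump in use until then.
- Table 2 sets out a 15-day study.
- The permanent home pump is arranged after the study ends.
- No step returns a mother to the standard pattern after 7 days.

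These agree with each other and with the primary window, so 7 days is the likelier slip.

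**Sample size.** The stated 80% power reproduces. With 30 per group, two-sided alpha 0.02 and the stated effect size 0.84, the noncentrality is 0.84 × √(30/2) = 3.25 on 58 degrees of freedom, and the two-sample t-test has 80.25% power. Correcting the duration changes none of these inputs.

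**CTV.** Take a mother who first reaches 500 mL on day 15. She fails under the day 14 definition and may succeed under day 14-15. Only such mothers are affected, and the protocol gives no basis for counting them.

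**The case against.** The best defence is that 7 days is shorthand for the week from day 8 to day 15. That works as elapsed days for a day 8 start, and SMART data are taken only from day 8. The operational text also settles practice: the SMART pump replaces the standard one, a card sets the pattern, a matching pump is placed at the bedside, and recording runs to day 15. To stop at 7 days, staff would have to invent a step. Much of this stands. It limits the contradiction to day 6 and 7 starts, plus at most one day for day 8 starts, and it makes the harm conditional. It does not remove the contradiction, because the protocol expressly allows the pump change on day 6 or 7 and never says the pattern begins on day 8 or continues to day 15.

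It is also fair to say that use through day 15 is inferred, and that some support is weak. Pump return appears among the conditions for the last payment, beside a mood questionnaire due at day 15, but the return itself is not dated. The description of a 2-week study in Possible Benefits fits day 14 as well as day 15.

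A reader might go further and infer that the primary comparison is diluted, biased or underpowered. The documents do not support that. They describe no switch-back and give neither the distribution of start days nor any carry-over, so no dilution can be sized. Start day is fixed at or before allocation, so it is balanced across arms in expectation.

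A reader might also take the CTV mark in Table 2 as a third cut-off, at day 15. The column position is uncertain in the text at hand, and a mark there could simply show when the day 14 total is assessed. Daily volumes are weighed for all 15 days, so either CTV definition can be computed. The conflict concerns which one counts.

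**Conclusion.** The contradiction is real and should be fixed, but its reach is limited. Taken literally, 7 days leaves 2-3 of the 8 primary window days off pattern for a day 6 start, 1-2 for a day 7 start and 0-1 for a day 8 start. The range in each case is the difference between the elapsed and calendar counts. How many mothers fall in each group cannot be told from the protocol.

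The conclusion that 7 days is the error rests on inference from the recording windows, the timeline and the absence of a switch-back. If the pump is kept to day 15, every window day is on pattern, and neither exposure nor power is lost. The remaining fault is then that the protocol understates use by 1 to 3 days (8, 9 or 10 days against 7). Off-pattern days enter the primary outcome only if staff apply the written duration.

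The two CTV cut-offs are a genuine but minor inconsistency in a secondary outcome.

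**What to change.** In the Abstract and the Randomization paragraph, replace the 7-day duration with: from randomisation (day 6-8) through postpartum day 15. Add that exposure therefore varies from 8 to 10 calendar days with start day. Keep the day 8-15 window.

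Starting every mother's pattern on day 8 would also reconcile 7 elapsed days with the window, but it would change the pump hand-over now set at day 6-8. The wording change is simpler and matches the schedule.

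For CTV, use the explicit definition, at least 500 mL/day by day 14, wherever the outcome is named: the Abstract's outcome list, the Background and Aim 2 under Specific Aims. Check that the Table 2 entry agrees.

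The cost is wording only. Volumes are already weighed daily for 15 days and SMART recording already runs to day 15, so no new data, visits or pumps are needed and the sample size is unchanged.

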## Research Procedures and Analyses by Specific Aim.

**Aim 1**: *The primary aim of this study* is to compare the clinical effectiveness of 3 different BPSPs on pumped milk volume during Days 8-15 postpartum.

Mothers will have access to a hospital grade breast pump (Medela Symphony Plus) while hospitalized and when visiting their infant in the NICU (standard policy). Upon hospital discharge, all mothers will be provided the same hospital grade breast pump for home use. At 6-8 days postpartum, those mothers who undergo randomization, will be provided a hospital grade SMART pump (Medela, AG, Switzerland) as a substitute for the standard hospital breast pump. The SMART pump (the same breast pump used as standard care) has been adapted to electronically measure, record and store both pumping behaviors and weighed MOM volume (measured ± 0.1g; 1 g=1 mL). A card will be inserted into the SMART pump which will program the pump to either use BPSP1, BPSP 2, or Standard Plus). Mothers will be blinded to the BPSP used. Information is stored and the embedded computer chip is downloadable into a customized computer program (on a secure College of Nursing computer) at the termination of data collection. A SMART pump with the same randomized pattern will also be placed at their infant's bedside in the NICU to facilitate pumping in the NICU. Mothers will be provided a key tag to use prior to using the SMART pump to ensure only her pumping information is stored on the embedded computer chip. All mothers will be assisted to obtain a permanent breast pump for home use after study completion as per usual hospital care. Mothers that have been withdrawn from the study, at week 1, for not reaching SA, will be allowed to use the Medela Symphony Plus for 2-weeks, as needed.

Pumped milk volume will be measured daily using the following two method;

- (1) Mothers will weigh each bottle of MOM using the SMART pump and this information will be recorded and stored (only those mothers who are randomized and only from day 8-15).
- (2) All mothers will be provided pre-weighed and labeled vials to place their MOM following each expression per NICU policy and asked to bring all expressed MOM to the NICU. It is standard care in this NICU that all MOM brought to the NICU is weighed and the volume recorded in the infant's EMR (all mothers). Volume of pumped MOM will be determined by weight (1 mL = 1 gram). All MOM will be weighed by human milk technicians who have worked in this NICU's designated Human Milk Room since 2013, are not involved with direct care of either mother or infant and will be blinded to the group assignments. There are currently 7 human milk technicians covering the Human Milk Room 24/7 who

weigh and log each container of MOM delivered to the NICU. After MOM is weighed, it is available for infant consumption. Measurement of MOM volume (through weighing) will occur daily for 15 days. Although highly unlikely due to immaturity, if an infant breastfeeds, test weighing will be used to calculate volume of MOM consumed. Test weighing or weighing infants prior to and following breastfeeding, is an accurate method of determining intake during breastfeeding. Prior to each breastfeeding session, infants will be weighed. Weight will include clothing, diaper, and blankets worn by the infant. Following breastfeeding, the infant will be weighed again, clad in the same clothing on a Baby Weigh scale (Medela, Inc., McHenry, Ill) to the nearest 0.2g. Differences between pre- and post-feeding weights will be recorded in the infant's EMR and added to the total volume the mother expressed on that day.

**Aim 2:** A second aim will compare lactation outcomes including 1) maintenance of secretory activation, 2) rate of increase in daily pumped MOM volume, 3) whether or not mothers reach coming to volume (CTV; pumped milk volume of  $\geq 500$  mL by day 14 postpartum). daily pumped MOM volume, 4) cumulative MOM volume over days 1-7 and 8-15) milk removal efficiency, and 5) lactation duration.

**Maintenance of secretory activation**. For all mothers enrolled in the study, maintenance of secretory activation will be defined as a daily MOM sodium level < 20mM. A research assistant, blinded to group assignment, will collect 0.3 mL of MOM daily from

vials of MOM brought to the NICU and place the sample onto the sensor of an ion selective electrode analyzer (HORIBA, Japan) which is a hand-held machine used for sodium and potassium analysis (see photo), has been validated for accurate analysis of human milk sodium and potassium levels, and will be calibrated prior to every analysis. Although both sodium and potassium are secreted into milk via transcellular pathways, sodium but not potassium is also transferred from the maternal circulation via patent paracellular pathways. Thus, it has been suggested that a milk sodium to potassium ratio would standardize sodium level for individual women. While no differences have been reported between the ability of sodium alone versus a Na:K ratio to predict pumped milk volume, we will also measure potassium levels. (Appendix H) To ensure accuracy, individuals performing sodium analysis will be trained and evaluated prior to beginning analysis and quarterly. Our team is highly skilled in milk collection, processing and analysis.

Rate of increase in daily pumped MOM volume, achievement of secretory activation (Yes/No), and cumulative MOM volume over days 1-7 and 8-15 postpartum. MOM volume will be measured as discussed in Aim 1 and each of the outcomes determined.

Milk removal efficiency. Efficiency of milk removal will be determined by mls of MOM pumped per minute of pumping (cumulative per day and cumulative over days 8-15). Minutes of pumping is measured and recorded on the SMART pump (Appendix M).

Lactation Duration. Number of days a mother lactates (either via breastfeeding or expressing MOM) during her infant's hospitalization and whether or not she is lactating at infant discharge will be collected. Mothers will be determined to have ceased lactation when they are no longer bringing MOM to the NICU, are not placing the infant to breast for nutritive or non-nutritive sucking, and states they are no longer lactating when questioned. If still lactating at their infant's NICU discharge, mothers in all groups will be questioned regarding their continued lactation through monthly text message hyperlinked surveys via the Qualtrics platform until their infant is 6 months of age or she has ceased lactation. If a mother ceased lactation within the past month, she will be asked the week within the past month she discontinued lactating (Appendix J).

**Aim 3:** Will compare maternal perceptions of comfort, effectiveness, efficiency, and convenience of the 3 different breast pump patterns.

Mother's perception regarding the comfort, rhythm, effectiveness, and ease of use of the three BPSPs will be assessed via a text message hyperlinked Qualtrics survey within 7 days of study completion. A reminder will be sent if no response in 7 days (Appendix K).

**Aim 4:** A fourth aim will compare proportion of feedings consisting of MOM consumed by infants between the 3 groups. Daily proportion of total feeds consisting of MOM consumed during the first 15 days and proportion of total feeds consisting of MOM consumed during the 24 hours prior to discharge will be recorded from the infant's EMR. Proportion of feeds that include MOM after discharge will be determined until the mother ceases lactation or the infant is 6 months old through monthly text message hyperlinked surveys through Qualtrics asking the total number of feeds in the past 24-hours that consisted of MOM (either direct breastfeeding or feeding expressed MOM).

**Exploratory Aim 1**: Will explore potential benefits of the three BPSPs on the lactation outcomes in Aim 1 and 2 of mothers with co-morbidities known to negatively affect lactation outcomes (high BMI/obesity, diabetes, pregnancy induced hypertension).  A subset of mothers diagnosed with high BMI/obesity, diabetes, and/or pregnancy induced hypertension will be classified as having 1, 2, or 3 risk factors known to negatively affect lactation outcomes. Potential benefits of the three BPSPs will be explored in this subset of mothers.

Exploratory Aim 2: Explore whether mothers identified as having faltering lactation who use an alternate BPSP (BPSP 1 or 2) achieve the same lactation success as mothers identified as not having faltering lactation (pumped MOM volume  $\geq 350$  mL/d by day 6-8). Lactation outcomes (see Aim 1 and 2) will be compared between mothers who were randomized to use either BPSP 1 or 2 and those mothers who were not randomized because they were not identified as having faltering lactation.

Confounding Variables. The following variables may affect pumped MOM volume in mothers of critically ill infants. While control of these variables within the study is impossible, we will carefully document these factors on all enrolled mothers to allow for inclusion in statistical analysis as adjustment variables. See **Table 1** for additional confounding variables.

Skin-to-skin care: Episodes and duration of skin-to-skin care (holding infants dressed in a diaper on their mother's bare chest) will be documented by bedside nurses and data collected from the infant's EMR. Skin to skin care has been associated with increased MOM production in observational studies,  yet the frequency or duration needed is not known, and skin-to-skin care may not be possible due to an infant's critical status.  Skin-to-skin care is encouraged in this NICU and nursing protocols are in place to provide support to all mothers. When stable and of appropriate maturity, infants too immature to orally feed are encouraged to suckle at an empty breast during skin-to-skin care and the number and duration of these episodes will be collected.

Lactation Support: Episodes of lactation support will be documented by lactation consultants in the infant's EMR. Although lactation support may improve breastfeeding success, limited data exists regarding the effect of lactation support in pump dependent mothers of critically ill infants. There are 5 (3 FTE) lactation specialists providing services to mothers in the hospital and who evaluate all mothers prior to discharge and provide ongoing services to mothers whose infants remain in the NICU which is congruent with all mothers expressing MOM for infants in the NICU. Information regarding any lactation support mothers receive outside of UF Health will be determined through monthly surveys. If no response within 7 days, a one-time reminder will be sent (Appendix C; Appendix J).

Maternal Mood. Maternal mood affects breastfeeding success in healthy term infants and may impact lactation success in mothers of critically ill infants. Prior to hospital discharge, and at 15 days postpartum, all mothers will be asked to complete the MAACL-R; a standardized instrument with well-documented psychometric properties that assesses mood states by using positive and negative mood state scales for Anxiety, Depression, Hostility, Positive Affect and Sensation Seeking. It consists of 132 adjectives at  $\leq$  an  $8^{th}$  grade reading level,

takes approximately 3 minutes to complete. This test has been successfully used in lactating mothers of premature infants and in our previous studies.  While not designed to identify individuals with anxiety or depression needing medical or psychological intervention, each test will include a letter providing detailed instructions and phone numbers on how to obtain assistance through the crisis hotline or UF Department of Psychiatry if mothers feel anxious or depressed. Mothers will have standard access to social workers who work in NICU to support all mothers during their infants NICU stay. (Appendix D and E).

